### **Clinical hypothesis.**

ATP contributes to the development of cough hypersensitivity in patients by enhancing the neural activations mediated by vagal pathways involving jugular ganglia sensory neurons.

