However, it is important to note that this work has only been conducted on neurons from healthy animals, and as such how ATP dependent responses at the neuronal level changes in pulmonary disease is not entirely clear.

***Consequently, the role of nodose versus jugular afferent pathways in human chronic cough dependent upon purinergic mechanisms remains unclear.***

The differential organization of nodose and jugular neurons within the central nervous system may allow insights into the relative contribution of nodose and jugular afferent pathways in ATP-dependent cough in health and disease. Thus, axonal guidance cues under the regulation of placodal transcription factor Phox2b attract nodose terminals to the medullary regions of the nucleus of the solitary tract (nTS) (23). By contrast, the [name] group have recently shown that the neural crest derived jugular ganglia neurons have their central terminations in the trigeminal nuclear complex, in a little-known region called the

**Fig 1.** Pulmonary jugular (red) and nodose (green) vagal sensory pathways are anatomically and functionally distinct.

paratrigeminal nucleus (Pa5) (24, 25). Thus, in rats and guinea pigs injection of a retrograde tracing dye into the nTS labels only neurons in the nodose ganglia, while a comparable injection in the Pa5 labels only jugular neurons. Because of this differential brainstem wiring, the ascending pathways in receipt of nodose and jugular afferent inputs are also different (24). *Until now, this has been impossible to study in humans. Consequently, we know nothing about the neural mechanisms involved in ATP dependent cough in humans, nor do we know how these neural processes might behave in patients with chronic cough.* This issue is central to the current funding request because our team

has optimized methods for assessing cough neural circuit activation driven by ATP in humans (see preliminary data) and are positioned to make major insights into these neural processes.

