We have generated functional brain imaging (fMRI) data to suggest that the different brain circuits in receipt of nodose and jugular ganglia neuron inputs (as identified in animal studies) are conserved in humans. When inhaled, the tussigenic compound capsaicin (from hot chili peppers) indiscriminately stimulates both nodose and jugular chemosensitive afferents and we have published that capsaicin inhalation produces brain activations in the primary sensory, anterior and mid-insula, cingulate, premotor, motor and orbitofrontal cortices (29, 30). These regions are presumed to encode perceptual awareness of airway irritation, and the associated emotional, cognitive and behavioral (motor) consequences. For example, activity in the human primary sensory cortex (which receives jugular ganglia inputs in animal studies) correlates with an individual's perception of airway irritation (their perceived need/ urge to cough) while activity in the insula (in receipt of nodose inputs) relates closely to the actual magnitude of the delivered stimulus independent of perception. We have now built upon these published findings by using high resolution brainstem fMRI during the inhalation of ATP (expected to only activate P2X2/3 expressing nodose-derived airway afferents) versus capsaicin (expected to activate both jugular and nodose chemosensitive afferents). Our results are striking and reveal that ATP inhalation evokes an increased signal level in the brainstem regions corresponding to the nTS, while capsaicin inhalation produces activations in both the nTS and in an area of the dorsal spinal trigeminal nucleus on the lateral margins of the brainstem that contains the paratrigeminal nucleus (Fig 2). Indeed, our healthy participants did not cough as much to ATP compared to capsaicin, consistent with studies of cough in animals and humans and the relatively poor cough-evoking properties of ATP in healthy humans (20, 21). However, the perception of airway irritation was identical between ATP and capsaicin stimuli (Fig 3). We believe that cough production will ultimately be dependent upon activation of the neural circuit that integrates in the paratrigeminal nucleus (i.e. the jugular afferent pathway) and therefore

***we hypothesize that there is an upregulation of the capacity of ATP to act via jugular ganglia pathways in chronic cough patients.***

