The fMRI studies described above provide an exciting opportunity to assess for the first time which primary airway afferent pathways are likely excited or sensitized by ATP and, in turn, what aspects of the central processing of airway sensory information is altered by ATP. We have reported previously that patients with chronic cough display functional brain responses consistent with a state of central sensitization (10) that closely resembles the central sensitization accompanying chronic pain (31).

***We will extend upon these findings by determining whether ATP-sensitive pathways in the brainstem and brain are altered in patients with chronic cough, and in doing so provide insight into whether ATP effects vagal afferent processing through an interaction with nodose and/ or jugular neural pathways.***

[figure not shown]

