facemask fabricated to deliver stimuli through oral breathing (and to be compatible for hands free use in an MRI scanner). Doubling doses of stimuli are used throughout the study ranging from 0.06 $\mu$ M to 125 $\mu$ M for capsaicin and 0.45 – 232.5mM for ATP. Once the C2 dose is identified, participants will receive randomized challenges with doses two increments above and below the C2 (C2-2, C2-1, C2, C2+1 and C2+2) to accurately measure the stimulus response function for each individual. Finally, in preparation for fMRI scanning, participants will be challenged for 24 seconds with stimuli above and below the C2 dose to determine challenge stimuli doses that are tolerable for brain imaging (defined as the Smax). This session is used to ascertain each participant's sensitivities and tolerances to inhaled stimuli and to inform the participants about the design of the subsequent fMRI session.

In the second session, participants return for fMRI scanning. Structural and functional MRI data are collected on a Siemens Magnetom Trio 3 Tesla scanner (Siemens AG, Erlangen, Germany) with a 32-channel head coil located at the Monash Biomedical Imaging Facility, Melbourne, Australia. Anatomical T1 - weighted images are acquired in the sagittal plane (192 slices, 0.90 mm slice thickness, 0.84  $\times$  0.84 mm^2 in - plane resolution, echo time (TE) = 2.59 ms, repetition time (TR) = 1900 ms, flip angle = 9). Two functional MRI (fMRI) scans of 491.4 seconds duration are performed using the BOLD contrast. Functional runs are collected using a partial field of view (FOV) with a gradient-echo echo-planar parallel imaging sequence (GRAPPA, PAT factor=3, reference lines=36, TR=1790ms, TE=30ms, 27 slices, 2.5mm thickness, 1.88mm in-plane resolution, flip angle=70 degrees). This facilitates a restricted focus on the brainstem necessary to define regional activations in this area (see Figure 2).

During image acquisition, participants lay comfortably on the scanner bed with their head stabilised with foam padding and hearing protection. Participants are fitted with the facemask and apparatus used in the psychophysical testing session. Online respiratory monitors are fitted around their chest throughout the experiment (AD Instruments). A periscope mirror attached to the scanner head coil enables participants to view a projector

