### *Variables/Time Points of Interest*

Two types of data will be collected, (1) Blood Oxygen Level Dependent signal data collected during fMRI scans and used to determine regional brain activity, and (2) psychophysical data during preliminary testing sessions and during fMRI scanning. The latter includes the stimulus dose evoking 2 coughs (C2), the stimulus dose required for the initial detection of an urge to cough (Cu) and the maximal suppressive stimulus dose where a participant can resist coughing (Smax). As part of the clinical work up of the patients we will also collect

subjective patient scores of their cough severity and quality of life, using validated tools (the Leicester Cough Questionnaire (LCQ)) which can be also used to help interpret fMRI data. The primary variable of the study is the stimulus delivered (ATP versus capsaicin) compared between cough patients and healthy controls, assessing the differential outcomes on BOLD signal changes and associated psychometrics.

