### *Statistical Methods*

Statistical analysis of psychophysical parameters will be performed with SPSS 22.0. Independent t- tests will be used to test the effects of group on C2, Cu and Smax thresholds. A repeated-measures ANOVA is used to test the effects of group, dose and their interaction on urge-to-cough ratings in response to random stimulus challenges. Independent t-tests will be used to assess group effects on capsaicin/ ATP doses and urge-to-cough ratings associated with the fMRI scanning.

fMRI image analysis will be performed with FEAT, version 5.98. Regressors for each dose of capsaicin/ ATP and rating events will be included in a general linear model that also includes motion parameters and confound variables to take account of physiological noise. Contrasts for capsaicin/ ATP doses will be averaged across the three scans for each participant and used in the analysis of group and between-group effects. Group contrasts include high doses for all participants (Like-Behaviour), and activation levels will be tested for correlations with Cu and frequency of coughing during repeated stimulus challenges. Higher level analyses will be carried out for inter-group averaging and between-group comparisons. Z (Gaussianised T/F) statistic images are thresholded to define clusters of contiguous voxels activated at a significance level of  $Z > 2.3$ . To correct for multiple comparisons, a corrected cluster probability threshold (based on Gaussian Random Field Theory of  $p < 0.05$ ) is applied. Between-group contrasts are made using two different comparisons: i) during the inhalation of Smax for all individuals in both groups (matched urge-to-cough sensation). Activation levels associated with Smax doses are tested for relationships with the Cu threshold and the frequency of coughing during the psychophysical sessions.

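### The imaging analysis defines no nTS or paratrigeminal region and never compares the two, so it cannot support a claim of jugular rather than nodose change

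*Combined protocol and SAP*

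**What the plan says.** The Rationale states the open question: "the role of nodose versus jugular afferent pathways in human chronic cough dependent upon purinergic mechanisms remains unclear". Preliminary Data sets the aim of learning "whether ATP effects vagal afferent processing through an interaction with nodose and/ or jugular neural pathways" and gives the directional hypothesis: "we hypothesize that there is an upregulation of the capacity of ATP to act via jugular ganglia pathways in chronic cough patients". The Clinical hypothesis section likewise speaks of ATP "enhancing the neural activations mediated by vagal pathways involving jugular ganglia sensory neurons". Rationale and Preliminary Data tie the nodose pathway to the nTS and the jugular pathway to the trigeminal area that contains the paratrigeminal nucleus.

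Variables/Time Points of Interest says: "The primary variable of the study is the stimulus delivered (ATP versus capsaicin) compared between cough patients and healthy controls". This has a stimulus factor and a group factor but no region factor.

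For BOLD data, Statistical Methods plans group and between-group maps in FEAT, in which "statistic images are thresholded to define clusters of contiguous voxels" at Z > 2.3 with a cluster-corrected p < 0.05. It adds correlations of activation with Cu and cough frequency. Two between-group comparisons are announced and one is written out (at Smax). No nTS or paratrigeminal region appears. The other group tests there (t-tests and a repeated-measures ANOVA) concern cough thresholds, doses and urge-to-cough ratings. Power/Sample Size, by contrast, is calculated on regions of interest from the preliminary data.

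**The concern.** The question is about two named relays, but the imaging inference names neither. Two gaps follow.

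First, a surviving cluster shows that there is a group difference somewhere within it. It does not assign that difference to one small nucleus inside the outline.

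Second, nothing compares the relays. If a cluster falls over one and not the other, it is tempting to read this as a selective pathway change, but a significant result beside a non-significant one is not evidence that the two differ. The documents supply a rival explanation themselves: Background describes exaggerated responses to sensory input in patients, and Preliminary Data refers to central sensitisation. Patients could respond more in both relays.

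At stake is how the main conclusion may be worded. If regions are chosen or outlines interpreted after the maps have been seen, the choice cannot be made independent of the data later.

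**Working it through.** **The plan's own figure.** Power/Sample Size gives at least 80% power for 0.48 to 0.72 SD with 25 participants. Read as 25 per group, two-sample t, two-sided 5%, I get 38% at 0.48 and 70% at 0.72. The range is not reproduced. The plan states no alpha or sidedness, and fMRIpower has its own variance model, so the figure is unverified rather than shown wrong. The present point does not depend on it. What matters here is that it refers to regional differences that Statistical Methods never tests.

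**Illustration 1: reading one relay as passing and the other as failing.**

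- From the documents: 25 per group; effects of 0.48 to 0.72 SD.
- Assumed: the same true increase of 0.57 SD in both relays (inside the plan's range; 51% power per test), within-group correlation rho of 0.3 to 0.7 between the relays, and two separate two-sided 5% t-tests.

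Hand check at rho = 0: P(exactly one significant) = 2 × 0.51 × 0.49 = 50%. Positive correlation lowers this. Simulation of 40,000 studies:

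| rho | exactly one relay significant | only paratrigeminal | direct contrast significant |
|---|---|---|---|
| 0.3 | 41% | 20% | 5% |
| 0.5 | 34% | 17% | 5% |
| 0.7 | 26% | 13% | 5% |

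For the same correlations, exactly one relay is significant in 25 to 38% of studies at 0.48 SD and in 22 to 34% at 0.72 SD. The direct contrast keeps false dissociation at 5% throughout.

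**Illustration 2: how large a surviving cluster must be.** Study Design gives "27 slices, 2.5mm thickness, 1.88mm in-plane resolution", so a voxel is 1.88 × 1.88 × 2.5 = 8.84 mm³. Smoothness F and search volume V are not given and are assumed. The usual random-field approximation at u = 2.3 is:

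- E[m] = (V/F³)(4 ln 2)^1.5 (2π)^−2 (u² − 1) exp(−u²/2)
- E[N] = V(1 − Φ(u))
- β = (Γ(2.5) E[m]/E[N])^(2/3)
- critical extent k = (ln(E[m]/−ln 0.95)/β)^1.5

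With V = 25,000 mm³ and F = 4 mm: E[m] = 13.9, E[N] = 268, β = 0.168, k = 192 mm³, about 22 voxels, equal to a sphere 7.2 mm across.

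| F | V = 25 cm³ | V = 700 cm³ |
|---|---|---|
| 3 mm | 101 mm³ | 188 mm³ |
| 4 mm | 192 mm³ | 387 mm³ |
| 5 mm | 310 mm³ | 673 mm³ |
| 6 mm | 449 mm³ | 1,049 mm³ |

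The equivalent spheres are about 6 to 13 mm across. The documents give no spacing between the nuclei, so whether one cluster would cover both is unknown.

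**Power of the direct contrast.** For paratrigeminal minus nTS, the SD of the within-person difference is √(2(1 − rho)): 1.18, 1.00 and 0.77 for rho = 0.3, 0.5 and 0.7. With an effect in one relay only, 25 per group and two-sided 5%:

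| rho | 0.48 SD | 0.72 SD |
|---|---|---|
| 0.3 | 29% | 56% |
| 0.5 | 38% | 70% |
| 0.7 | 57% | 90% |

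**What the contrast removes.** An equal additive increase in both relays gives a contrast of zero. Under proportional gain g, with control responses a (paratrigeminal) and b (nTS), it is (g − 1)(a − b), which is zero only if a = b.

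**The case against.** The strongest reply is that the stated hypothesis is jugular involvement, not a larger change in the jugular relay than in the nodose one. The aim allows either or both: "through an interaction with nodose and/ or jugular neural pathways". An increase in both relays would not refute it, and the group-by-region contrast would be zero in that case although ATP's jugular action had risen. This stands, and it is why a test of the paratrigeminal response itself is needed as well as the contrast.

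Second, Preliminary Data reports that in healthy people ATP raised signal in the nTS, while capsaicin activated both areas. A paratrigeminal ATP response in patients would therefore be informative by itself. It would be, but a response below threshold in controls is not zero, and the finding would not show that the nTS changed less.

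Third, the capsaicin comparator can help to separate an ATP-specific change from generally larger responses. That is fair, though Statistical Methods does not write out such a contrast by region.

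Fourth, the simulation models two uncorrected regional tests that the plan does not list, and the plan nowhere says that one pass and one fail will be read as selectivity. Also correct: the percentages illustrate a misreading.

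Finally, the preliminary brainstem data did distinguish the two areas, and the restricted field of view was chosen for that purpose. This helps with description of location but does not change what a cluster p-value refers to.

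**Conclusion.** The concern holds in a limited form. The planned BOLD inference can describe where groups differ, and a paratrigeminal ATP cluster in patients would support the jugular hypothesis. It cannot support a statement that the jugular rather than the nodose pathway changed, because neither region is defined and the two are not compared.

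A reader might infer that no pathway conclusion of any kind is possible. The documents do not support that: the hypothesis concerns jugular involvement, on which a localised cluster is relevant evidence. A reader might also take 26 to 41% as the error rate of the stated analysis. It is not; it belongs to two separate 5% tests with equal true effects of 0.57 SD and assumed correlations of 0.3 to 0.7. The cluster sizes likewise rest on assumed smoothness and search volume.

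The logical point needs none of these assumptions. It does rest on the unwritten second between-group comparison not being a regional one; nothing in the text suggests that it is. This should be fixed before the group maps are examined, but it does not invalidate the study.

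**What to change.** Add to Statistical Methods:

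1. Fix an nTS mask and a paratrigeminal mask in advance, from anatomy and the independent preliminary data. Extract each participant's mean ATP and capsaicin response from unsmoothed or lightly smoothed data.
2. Test the group difference in the paratrigeminal ATP response as the test of the jugular hypothesis, and report the nTS result beside it.
3. Test the group-by-region contrast under ATP (paratrigeminal minus nTS, two-sided 5%). Make any claim of selectivity, such as a pathway shift, only on that result. Report the same contrast under capsaicin as a check on generally larger responses.
4. Use the cluster maps to describe location.

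The cost is SAP wording and a few hours of extraction and analysis, with no new participants or scans. There are two limits to state in the plan. The contrast has only 29 to 57% power at 0.48 SD and 56 to 90% at 0.72 SD for an effect in one relay, so a null result is not evidence of equal change. It also removes additive gain but not proportional gain, so it should be read beside the regional means.

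### The only imaging test is cluster extent, which cannot assign activity to the nTS or the paratrigeminal nucleus, can miss a strong focal effect, and is not the unit for which power is stated

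*Combined protocol and SAP*

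**What the plan says.** The question is set at the level of the nucleus. The Preliminary Data section states the hypothesis: "we hypothesize that there is an upregulation of the capacity of ATP to act via jugular ganglia pathways in chronic cough patients". It says the trial will "provide insight into whether ATP effects vagal afferent processing through an interaction with nodose and/ or jugular neural pathways". The anatomical markers are the nTS for nodose input and, for jugular input, "an area of the dorsal spinal trigeminal nucleus on the lateral margins of the brainstem that contains the paratrigeminal nucleus".

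Study Design chooses a partial field of view with "27 slices, 2.5mm thickness, 1.88mm in-plane resolution", on the ground that "This facilitates a restricted focus on the brainstem necessary to define regional activations in this area".

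Statistical Methods says "fMRI image analysis will be performed with FEAT, version 5.98", and then gives one inferential rule for the maps: "statistic images are thresholded to define clusters of contiguous voxels activated at a significance level of" Z > 2.3, followed by "a corrected cluster probability threshold (based on Gaussian Random Field Theory of" p < 0.05. It names no brainstem mask, smoothing kernel, small-volume correction, peak-height test or between-group region-of-interest test. Multiplicity is marked as not applicable. Power/Sample Size rests on signal extracted from regions of interest and states at least 80% power for 0.48 to 0.72 SD between groups.

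**The concern.** Three things do not fit together.

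- **Localisation.** A cluster p-value rejects the statement that there is no signal anywhere in the cluster. It does not say which part is active. If a cluster covers or adjoins both areas, nothing in the plan licenses calling it jugular rather than nodose.
- **Sensitivity.** A cluster must reach a minimum size however high its peak, so a strong effect confined to a small nucleus can be reported as absent.
- **Unit.** Power is stated for region-of-interest signal, but the test that will be run is on clusters. The power figure does not carry over.

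All three bear on the main conclusion, whether ATP recruits the jugular pathway in patients. None concerns the false-positive rate of the Z > 2.3 rule. They would hold if that rate were exactly 5%.

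**Working it through.** **1. The plan's own figure.** With 25 per group, a two-sample t-test has 48 df and noncentrality d × √(25/2) = 3.536d. At d = 0.72 this is 2.55, and power is 0.81 one-sided at 5% or 0.70 two-sided. At d = 0.48 it is 1.70, and power is 0.51 or 0.38. Only the upper end reproduces, and only one-sided. The fMRIpower inputs, alpha and sidedness are not given, so this is a separate matter. It is used here only to place the planned effect at an expected Z of about 1.7–2.5.

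**2. Minimum cluster size.** From the documents: u = 2.3, p = 0.05, voxel volume 1.88 × 1.88 × 2.5 = 8.84 mm³. Assumed, because not stated: FWHM F, search volume V, and thresholding on the acquired grid.

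- Expected clusters: E[m] = (V/F³)(4 ln 2)^1.5 (2π)^−2 (u² − 1) exp(−u²/2)
- Expected voxels above u: E[N] = (V/8.84) × 0.0107
- β = (Γ(2.5) E[m]/E[N])^(2/3)
- k = [ln(E[m]/0.0513)/β]^1.5, where 0.0513 = −ln 0.95

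For V = 35 mL and F = 3 mm: E[m] = 46.2, E[N] = 42.5, β = 1.278, k = (6.80/1.278)^1.5 = 12.3 voxels.

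| FWHM (mm) | 35 mL | 600 mL |
|---|---|---|
| 3 | 12.3 | 20.7 |
| 4 | 23.7 | 42.7 |
| 5 | 38.8 | 74.0 |
| 6 | 56.8 | 115.2 |

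The wider range runs from 6 voxels (3 mL, 3 mm) to about 240 (800 mL, 8 mm). Using u² in place of u² − 1 gives 10.4 and 97.3 at the two corners of the table. At 3 mm the formula expects more clusters than voxels above threshold, so that row is only indicative.

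**3. Detection of a small focus.** Assumed: a 7-voxel focus, a 36 mL mask, smooth Gaussian noise, 600 fields per setting, and random-field thresholds for both rules.

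| FWHM (mm) | Cluster, Z = 5 | Peak height, Z = 5 | Cluster, Z = 6 | Peak height, Z = 6 |
|---|---|---|---|---|
| 3 | 16% | 62% | 30% | 91% |
| 4 | 10% | 70% | 18% | 94% |
| 5 | 11% | 73% | 16% | 95% |
| 6 | 15% | 80% | 22% | 96% |

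With the 600 mL threshold, the cluster rule finds the Z = 6 focus in 1–2% of fields. At Z = 6, when the 36 mL cluster rule does detect the focus, on average 56%, 77%, 86% and 91% of the significant cluster lies outside it, at 3, 4, 5 and 6 mm.

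**4. What those peaks mean.** Z = 5 corresponds to 5/3.536 = 1.4 SD between groups (1.6 SD after converting t on 48 df to Z). Z = 6 corresponds to 1.7 SD (2.1 SD after conversion). The plan expects 0.48–0.72 SD.

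**5. At the planned effect.** In further runs at expected Z of about 1.7–2.5, voxel-level control finds 2- and 7-voxel foci in about 1–25% of maps. For larger sources at 3 mm and Z = 2.5 the cluster rule is better: 65% versus 36% for 40 voxels, and 98% versus 52% for 80 voxels.

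**6. A region-of-interest test.** This uses the t-test of step 1, two-sided, with Bonferroni levels for two tests (two regions, one stimulus) and four tests (two regions, two stimuli). Holm is at least as powerful for each test.

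| Two-sided alpha | Power at 0.48 SD | Power at 0.72 SD |
|---|---|---|
| 0.05 | 38% | 70% |
| 0.025 | 28% | 59% |
| 0.0125 | 20% | 49% |

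**The case against.** The strongest reply is that the numbers rest on inputs from outside the documents. Mask, smoothing, group-grid resolution, nucleus volume and the distance between the nuclei are all unstated. With a small-volume mask of 3–6 mL at 3 mm the minimum falls to 6–8 voxels, and the gap to a few-voxel nucleus nearly closes. Spread into a neighbouring nucleus is also sensitive to the assumed distance. At 4 mm apart it occurs in 30–79% of detections at 3 mm smoothness and 84–100% at 5 mm. At 6–8 mm apart it falls to about 0–5%. No matching rate was computed for voxel-level control. The comparison also depends on calibration: for a 20-voxel source at 5 mm and Z = 5, an exact cluster threshold detects 63%, against 42% with the random-field one.

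This stands, so the voxel counts and percentages are illustrations. It also stands that the striking detection gaps belong to effects two to four times the planned size, and that replacing the cluster rule with voxel-level control would give up real sensitivity to extended activation.

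The reply does not touch localisation, which needs no assumed figure, or the mismatch between the unit tested and the unit powered. The plan does mention correlating activation levels with cough measures, but that is not a between-group test in a named nucleus.

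**Conclusion.** The point holds in a limited form. Cluster extent as the only imaging inference cannot support a nucleus-level conclusion. It can miss a strong focal effect, and it is not the test for which power is stated. The first and third statements follow from the documents alone. The second is supported under the assumptions shown.

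Three stronger readings are not supported:

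- A reader might infer that the plan requires 12–115 contiguous voxels. It states no minimum, and that range is two corners of an assumed grid.
- A reader might infer that the trial will miss paratrigeminal activation. Preliminary Data reports capsaicin activation in an area containing that nucleus, though without a threshold and not as a patient–control difference. Only can miss is justified.
- A reader might infer that voxel-level control would rescue the planned effect. At 0.48–0.72 SD it is weak for small foci as well.

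This is a cheap improvement, not a fatal flaw.

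**What to change.** In Statistical Methods:

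- Make the confirmatory brainstem test a between-group comparison of mean BOLD signal in two regions fixed in advance, the nTS and the paratrigeminal area.
- Correct across the regions and stimuli tested, for example by Holm, and put this under Multiplicity in place of the not-applicable entry.
- Fix the brainstem mask and the smoothing kernel, with smoothing near the voxel size.
- Attribute activity to a nucleus only from these region tests, or from voxels that survive voxel-level family-wise control within that mask.
- Keep the cluster-extent map for detecting extended activation, without using it to name a nucleus.

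In Power/Sample Size, restate power for the test actually run, with alpha and sidedness.

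The cost is wording and a re-run of the group-level step, with no new data. The regions must be drawn before analysts know group membership. The multiplicity cost at 0.72 SD is a fall in two-sided power from 70% to about 59% for two tests, or 49% for four at the Bonferroni level.
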